9.3 High-throughput sequencing of CDR3 from IgH, IgK and IgL somatic rearrangements

Adaptive Biotechnologies have developed assays that use multiplex PCR to amplify rearranged CDR3 sequences from the adaptive immune receptor loci (T-cell receptors in T-cells, Immunoglobulins in B-cells) that exploit the capacity of high-throughput sequencing technology to sequence thousands to millions of CDR3 chains simultaneously in a sample. At all IG loci, forward primers were selected for each V segment, upstream of the recombination signal sequence (RSS), and reverse primers were selected for each J segment, downstream of the RSS. In the IGH assay forward primers are also selected upstream of the D segments, allowing for amplification of immature DJ rearrangements (Fig 1C). In the IGK assay a forward primer is also selected for iRSS, and a reverse primer for KDE, allowing for amplification of iRSS/KDE and V/KDE junctions (Fig 1H), as well as VJ CDR3 segments. The forward and reverse primers for each locus are separated by many thousands of base pairs in the germline, but each somatic rearrangement event brings one pair within 300 bp. The multiplex PCR reaction amplifies only these rearranged sequences, and incorporates external adaptor sequences allowing the amplified library to be directly sequenced.

[figure not shown]

Figure 1: Somatic rearrangement of the IG loci.

Any multiplex PCR system is susceptible to amplification bias for specific templates, so they designed a panel of synthetic templates representing all possible V/J pairings at each locus.¹⁰⁴ Amplification and sequencing from an equimolar mixture of these synthetic templates allows them to directly measure amplification bias. In both assays, primer amplification effects are independent for forward and reverse primers, so primer concentrations are titrated to minimize amplification differentials within the assay, yielding a final primer mix that amplifies all synthetic templates with between 0.5X and 2X cumulative yield after 35 cycles of PCR, relative to the median yield. The residual differential in amplification efficiency is highly

reproducible within each assay, so the frequency of each sequence after amplification can be computationally adjusted for the specific forward and reverse primer that amplified that clone, yielding a direct estimate of the frequency of each clonal CDR3 rearrangement in the starting template material. If the high-throughput sequencing is performed on a sample containing one million nucleated cells, then its sensitivity in that circumstance is estimated to be 1 in a million.

Sequencing CDR3 regions:

IGH CDR3 regions can be amplified and sequenced from DNA samples. Amplification and sequencing of *IGH* CDR3 regions will be carried out on the *ClonoSEQ*TM platform (Adaptive Biotechnologies, Seattle, WA). The sequences for *IGH* CDR3 regions are delineated according to the definition established by the International ImMunoGeneTics collaboration.^{105,106} A standard algorithm is used to identify which V, D, and J segments contributed to each *IGH* CDR3 sequence and which V and J segments contributed to each CDR3 sequence.^{105,106} Rearranged CDR3 sequences are classified as non-productive if insertions or deletions were identified that resulted in frame-shifts or premature stop-codons.

Bone marrow samples (with CD138 selected DNA) will be obtained prior to autologous HCT, prior to the initiation of HCT, at cycle #6 of maintenance and after completion of planned panobinostat maintenance therapy to evaluate myeloma clones. To identify index myeloma clones, archived FFPE bone marrow clot sections (prior to start of systemic chemotherapy) will be obtained at Moffitt Cancer Center.

Table 9-1 Research Sample Acquisition Schedule

	Pre-HCT	Pre-maintenance	Cycle #1 (days 1, 5)	Cycle #2	Cycle #3	Cycle #6	Cycle #9	End of study
Peripheral blood	1 tiger top/6 green top	1 tiger top/6 green top	1 tiger top/6 green top (day 1); 2 green top (day 5)	1 tiger top/6 green top	1 tiger top/6 green top	1 tiger top/6 green top	1 tiger top/6 green top	1 tiger top/6 green top
Bone marrow	1 tiger top/4 green top	1 tiger top/4 green top	-	-	-	-	-	1 tiger top/4 green top
Stem cell graft (Apheresis)	3mL in a 50mL falcon tube	-	-	-	-	-	-	-

10 Safety monitoring

10.1.1 Definitions

Serious adverse event (SAE) is defined as one of the following:

- Is fatal or life-threatening

- Results in persistent or significant disability/incapacity
- Constitutes a congenital anomaly/birth defect
- Is medically significant, i.e., defined as an event that jeopardizes the patient or may require medical or surgical intervention to prevent one of the outcomes listed above
- Requires inpatient hospitalization or prolongation of existing hospitalization,
- Note that hospitalizations for the following reasons should not be reported as serious adverse events:
 - Routine treatment or monitoring of the studied indication, not associated with any deterioration in condition
 - Elective or pre-planned treatment for a pre-existing condition that is unrelated to the indication under study and has not worsened since signing the informed consent
 - Social reasons and respite care in the absence of any deterioration in the patient's general condition
- Note that treatment on an emergency outpatient basis that does not result in hospital admission and involves an event not fulfilling any of the definitions of a SAE given above is not a serious adverse event

10.1.2 Reporting

All SAEs will be reported as assessed by the investigator. SAEs will be followed until resolution or until clinically relevant improvement or stabilization.

To ensure patient safety, every SAE with suspected causality, occurring after the patient has provided informed consent and until at least 30 days after the patient has stopped study treatment must be reported to Novartis within 24 hours of learning of its occurrence.

Any SAEs experienced after this 30 days period should only be reported to Novartis if the investigator suspects a causal relationship to the study treatment. Recurrent episodes, complications, or progression of the initial SAE must be reported as follow-up to the original episode within 24 hours of the investigator receiving the follow-up information. An SAE occurring at a different time interval or otherwise considered completely unrelated to a previously reported one should be reported separately as a new event.

Information about all SAEs is collected and recorded on the Serious Adverse Event Report Form as outlined per contractual agreement; all applicable sections of the form must be completed in order to provide a clinically thorough report. The investigator must assess and record the relationship of each SAE to each specific study treatment (if there is more than one study treatment), complete the SAE Report Form in English, and send the completed, signed form by fax within 24 hours to the oncology Novartis Drug Safety and Epidemiology (DS&E) department.

The telephone and telefax number of the contact persons in the local department of Drug Safety and Epidemiology (DS&E) are included in the contractual agreement. The original

copy of the SAE Report Form and the fax confirmation sheet should be kept with the case report form documentation at the study site.

Follow-up information is sent to the same contact(s) to whom the original SAE Report Form was sent, using a new SAE Report Form stating that this is a follow-up to the previously reported SAE and giving the date of the original report. Each re-occurrence, complication, or progression of the original event should be reported as a follow-up to that event regardless of when it occurs. The follow-up information should describe whether the event has resolved or continues, if and how it was treated, whether the blind was broken or not, and whether the patient continued or withdrew from study participation.

If the SAE is not previously documented in the Investigator's Brochure or Package Insert (new occurrence) and is thought to be related to the Novartis study treatment, an oncology Novartis Drug Safety and Epidemiology (DS&E) department associate may urgently require further information from the investigator for Health Authority reporting. Novartis may need to issue an Investigator Notification (IN), to inform all investigators involved in any study with the same drug that this SAE has been reported. Suspected Unexpected Serious Adverse Reactions (SUSARs) will be collected and reported to the competent authorities and relevant ethics committees in accordance with Directive 2001/20/EC or as per national regulatory requirements in participating countries.

10.2 Pregnancies

To ensure patient safety, each pregnancy occurring while the patient is on study treatment must be reported to Novartis within 24 hours of learning of its occurrence. The pregnancy should be followed up to determine outcome, including spontaneous or voluntary termination, details of the birth, and the presence or absence of any birth defects, congenital abnormalities, or maternal and/or newborn complications.

Pregnancy should be recorded on a Clinical Trial Pregnancy Form and reported by the investigator to the oncology Novartis Drug Safety and Epidemiology Department (DS&E). Pregnancy follow-up should be recorded on the same form and should include an assessment of the possible relationship to the panobinostat any pregnancy outcome. Any SAE experienced during pregnancy must be reported on the SAE Report Form.

Pregnancy outcomes must be collected for the female partners of any males who took study treatment in this study. Consent to report information regarding these pregnancy outcomes should be obtained from the mother.

10.3 Data Safety and Monitoring Plan

The Data Safety & Monitoring Plan (DSMP) will ensure that this trial is well designed, responsibly managed, appropriately reported, and that it protects the rights and welfare of patients. The following internal and external review and monitoring processes provide oversight and active monitoring of this trial:

- The Principal Investigators (PI)

- The Scientific Review Committee (SRC)
- The Protocol Review and Monitoring Committee (PRMC);
- The Research Compliance Division (RCD) of the Cancer Center's Compliance Office;
- Institutional Review Board (IRB).

The protocol includes a section that specifies the following with respect to Adverse Event reporting: what constitutes an adverse event (versus what is a serious adverse event), the entities to which adverse events should be reported, the timing of this reporting, and the person or persons responsible for reporting. This includes prompt (within one day of knowledge of the event) reporting to the IRB for unanticipated risks to subjects and reporting in writing within five working days to the IRB and the supporting company (Novartis).

10.4 Initial and Ongoing Monitoring and Review

10.4.1 Principal Investigator (PI)

The PI of the study has primary responsibility for ensuring that the protocol is conducted as approved by the SRC and the IRB. The PI will ensure that the monitoring plan is followed, that all data required for oversight of monitoring are accurately reported to the Scientific Review Committee (SRC), Protocol Review and Monitoring Committee (PRMC) and IRB as required, and that all adverse events are appropriately reported.

10.4.2 The Scientific Review Committee (SRC)

The Cancer Center's internal Scientific Review Committee (SRC) provides for a formal internal peer review of all protocols and general scientific oversight of interventional clinical research. The Committee has a defined membership representing all of the major research divisions of the Cancer Center, including biostatisticians. All new protocol submissions must contain the required elements of the protocol, and must include a DSMP prior to approval by the Committee. The plan has to be appropriate for the phase and risk of the proposed study.

10.4.3 The Protocol Review and Monitoring Committee (PRMC)

The Protocol Review and Monitoring Committee (PRMC) will monitor this trial for safety, progress, protocol compliance, accrual, adverse event reporting, and data integrity. The membership of the PRMC includes physician representation from each program area and a biostatistician. In addition to the existing stopping rules, the PRMC is authorized to suspend a trial for non-compliance with a DSMP or as a result of audit findings deemed unacceptable.

The PRMC will report significant findings to the IRB, the supporting company (Novartis), and the applicable regulatory body. Interim meetings are scheduled to address specific issues that require immediate attention to ensure safety of research participants.

10.4.4 The Research Compliance Division of the Cancer Center's Compliance Office (RCD)

The Research Compliance Division (RCD) Office conducts internal audits of all clinical trials conducted at the Cancer Center and its affiliates. The purpose of the internal audit program is to:

1. Assure patient safety by monitoring compliance
2. Assure regulatory compliance by reviewing consent and adverse event reporting
3. Assure scientific value by monitoring accuracy and completeness of data collection
4. Monitor and coordinate research compliance activities associated with institutional and individual conflict of interest
5. Make recommendations for modification of research practices as necessary and provide education on issues that are critical to good research practices

Audits are conducted by the RCD in accordance with applicable regulatory standards. Investigator initiated trials, such as the one proposed here, receive the highest priority for audit. The RCD will conduct and report the findings of audits to the PMC in accordance with a protocol's annual review. The PRMC will determine the findings to be acceptable with minor deviations, acceptable with corrective action, or unacceptable with suspension or closure. The PRMC Chairperson will notify the IRB of the audit findings. The RCD will follow-up to ascertain whether corrective actions, which have been agreed to, are achieving the desired results. The PRMC will be informed of all significant open follow-up items. For those observations where no action has been taken, the Research Compliance Office will inform the PRMC and may conduct a focused audit.

11 Protocol amendments, or changes in study conduct

Any change or addition to this protocol requires a written protocol amendment that must be reviewed by Novartis and the investigator before implementation. Amendments significantly affecting the safety of subjects, the scope of the investigation or the scientific quality of the study require additional approval by the IRB. A copy of the written approval of the IRB must be provided to Novartis.

12 Data Review and Management

These requirements for approval should in no way prevent any immediate action from being taken by the investigator or by Novartis in the interests of preserving the safety of all patients included in the trial. If an immediate change to the protocol is felt to be necessary by the investigator and is implemented for safety reasons Novartis must be notified and the IRB must be informed immediately. Data review and management

Internal Monitoring Plan Data will be captured in Oncore, Moffitt's Clinical Trials Database. Regulatory documents and case report forms will be reviewed routinely by the MCC Clinical Research Monitoring Core for accuracy, completeness and source verification of data entry, validation of appropriate informed consent process, adherence to study procedures, and reporting of SAEs and protocol deviations according to MCC Monitoring Policies.

12.1 Data collection and monitoring

Investigators must enter the information required by the protocol onto Case Report Forms (CRFs) for unexpected grades ≥ 3 adverse events and serious adverse events. Additional data to be captured may be identified at the time of study activation or review by ongoing monitoring committees.

13 Statistical methods

13.1 Statistical methods and data analysis

This is an open label study of 2 different panobinostat maintenance dosing schedules after autologous HCT in patients with multiple myeloma. There are 2 cohorts and patients will be enrolled sequentially to cohort A, then to cohort B. The sample size is 30 patients for this trial (15 for each cohort). We expect that at least 2/3 of each cohort will complete 12 cycles of maintenance panobinostat (regardless of dose modification) and will be evaluable for the primary endpoint. The widths of 95% confidence interval (CI) are 0.356, 0.438, 0.487, 0.514, and 0.522 when the proportions of patients tolerating 12 cycles of maintenance are 0.9, 0.8, 0.7, 0.6, and 0.5, respectively.

A patient who withdraws from the study due to reasons other than death, disease progression or toxicity will be replaced and is considered as non-evaluable for primary endpoint. The proportion of patients tolerating the therapy will be reported with 95% CI. All 30 patients are eligible for secondary endpoints. We will compute the overall response rates before the transplant, after autologous HCT, and after the completion of maintenance therapy, and at best response. The OS and PFS will be estimated using the Kaplan-Meier method. We will also report the incidences of all grades and grade ≥ 3 toxicities. The two-sided 95% CIs for

proportion, and OS and PFS will be computed using the Clopper-Pearson method and the Greenwood formula, respectively. In addition, the frequency of B cell precursor as well as other cell subsets, and their 95% CI will be evaluated using t-distribution. If data do not meet normality assumption, the power transformation (e.g., log-transformation) will be conducted. Those patients who are not in CR before the transplant would be most suitable for T-effector activity analysis. This will be examined by the paired t-test or the Wilcoxon signed-rank test, depending on the data distribution.

Relative dose intensity (RDI) represents the ratio of the amount of a drug actually delivered [actual dose intensity (DI)] to the amount planned (planned DI). The purpose of calculating RDI is to evaluate whether the planned DI of a chemotherapy treatment was actually achieved which may suggest the feasibility of planned treatment regimen. There are multitude of reports demonstrating a correlation between RDI and survival in cancer treatment.

$$\text{RDI} = (\text{total dose received by the patient} = \text{mg}) / (\text{planned full dose of drug} = \text{mg})$$

Optimal RDI for maintenance therapy in multiple myeloma has not been fully defined though it would be a surrogate measure for treatment feasibility. We intend to calculate RDI on two cohorts both together and separately. Missed doses, dose reduction and dose delay will be reportedly per cohort. The investigator will review the tolerability as a whole for 2 different cohorts and report feasibility of each cohort.

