4.2 Secondary

- To evaluate the complete response rate to panobinostat maintenance therapy after autologous HCT.
- To determine the 2-year PFS and OS of autologous HCT followed by panobinostat maintenance therapy in patients with multiple myeloma.
- **Exploratory secondary objectives:**
 - To evaluate histone acetylation (H3 and/or H4) of peripheral blood mononuclear cells
 - To isolate and identify clonotypic B cell progenitors in multiple myeloma patients from the bone marrow, peripheral blood and stem cell grafts.
 - To evaluate T-cell immune response against known myeloma tumor associated antigens while on panobinostat maintenance.
 - To evaluate humoral immunity against pneumococcal serotypes included in the standard of care heptavalent pneumococcal conjugate vaccine, and to assess cellular immune responses against CRM adjuvant found in the heptavalent pneumococcal conjugate vaccine.
 - To evaluate minimal residual disease (MRD) after autologous HCT followed by panobinostat maintenance therapy using flow cytometry
 - To evaluate MRD after autologous HCT followed by panobinostat maintenance therapy using multiplex PCR for CDR3 sequences

5 Overall study design

This is an open-label trial to determine the safety and tolerability of 2 different dosing schedules of single agent panobinostat maintenance therapy in patients with multiple myeloma who underwent high-dose melphalan followed by autologous HCT in patients with multiple myeloma. It is unknown whether the toxicity profile of panobinostat will be accentuated in patients after autologous HCT in the setting of maintenance therapy, hence the dose chosen for maintenance therapy is lower than MTD dosing or other phase 2 studies. There are 2 dosing schedules evaluated in this protocol in order to assess optimal tolerable schedule for panobinostat maintenance therapy after autologous HCT. As secondary

objectives, we will evaluate response after completion of treatment, and 2-year PFS and OS. As correlative studies, we plan to evaluate MRD, and to assess clonotypic B cells following an autologous HCT. We also plan to evaluate T effector immune response after autologous HCT while on panobinostat maintenance therapy.

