6.1.3 Inclusion and exclusion criteria (for panobinostat maintenance)

Patients will be enrolled to the panobinostat maintenance therapy study after receiving autologous HCT. Patients must have baseline evaluations performed prior to the first dose of study drug and must meet all inclusion and exclusion criteria. Results of all baseline evaluations confirming eligibility must be reviewed by the Principal Investigator (or co-investigator) prior to enrollment of that patient. In addition, the patient must be thoroughly informed about all aspects of the study, including the study visit schedule and required evaluations and all regulatory requirements for informed consent. The written informed consent must be obtained from the patient prior to enrollment. The following criteria apply to all patients enrolled onto the study unless otherwise specified.

Inclusion criteria (for panobinostat maintenance)

1. Adult patients, age ≥ 18 years old
2. Ability to provide written informed consent obtained prior to participation in the study and any related procedures being performed
3. Histologically confirmed diagnosis of multiple myeloma
4. Meeting the criteria for symptomatic multiple myeloma (“CRAB” criteria – See **Appendix B**) before the initiation of systemic chemotherapy
5. Received high-dose melphalan (≥ 140 mg/m²) followed by autologous HCT based on the institutional guidelines and within +45 and +180 after autologous HCT at the time of panobinostat maintenance initiation.
6. Patients must have achieved at least PR prior to autologous HCT and must not have progressive disease (PD) prior to the initiation of maintenance therapy (See **Appendix C** for response criteria)
7. Patients must meet the following laboratory criteria (prior to the initiation of panobinostat maintenance):
 - ANC $\geq 1 \times 10^9$ /L
 - Hemoglobin ≥ 8 g/dl
 - Platelets $\geq 50 \times 10^9$ /L (without transfusion support)
 - Creatinine clearance ≥ 40 ml/min or serum creatinine $\leq 2.5 \times$ ULN
 - AST and ALT $\leq 2.5 \times$ ULN
 - Serum bilirubin $\leq 1.5 \times$ ULN
 - Albumin > 3.0 g/dl
 - Clinically euthyroid. Note: Patients are permitted to receive thyroid hormone supplements to treat underlying hypothyroidism.

8. Baseline (pre-HCT) MUGA or ECHO must demonstrate LVEF \geq the LLN of the institutional normal.
9. ECOG Performance Status of ≤ 2 or Karnofsky performance status $\geq 70\%$ (See **Appendix D** and **Appendix E**)

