8.2 Efficacy assessments

All subjects will be evaluated every 3 months with multiple myeloma restaging (standard of care) including serum protein electrophoresis (SPEP), urine protein electrophoresis (UPEP) and serum free light chains. Response assessment will be performed approximately at cycle 3, 6, 9, and 12 of maintenance panobinostat therapy. Responses will be classified by according to the IMWG response criteria (Appendix C).

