13.1.4 Secondary objective and hypothesis

The secondary objectives of the study are to evaluate following parameters in patients who receive panobinostat maintenance therapy after autologous HCT: overall response rate, best response rate, 2-year PFS and 2-year OS. The exploratory secondary objectives include evaluation of minimal residual disease, frequency of B cell precursors and immune subsets, protein acetylation, and immune response against pneumococcal vaccines and CRM. The association of minimal residual disease, B cell precursors, and immune response with response, PFS and OS will be evaluated using the Cox proportional hazards regression model.

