16.2 Appendix B: Criteria for Symptomatic Multiple Myeloma

All three required:

1. Monoclonal plasma cells in the bone marrow $\geq 10\%$ and/or presence of a biopsy-proven plasmacytoma
2. Monoclonal protein present in the serum and/or urine^a
3. Myeloma-related organ dysfunction (1 or more)^b
 - (C) Calcium elevation in the blood (serum calcium > 10.5 mg/L or upper limit of normal)
 - (R) Renal insufficiency (serum creatinine > 2 mg/dL)
 - (A) Anemia (hemoglobin < 10 g/dL)
 - (B) Lytic bone lesions or osteoporosis^c

*Note: These criteria identify Stage IB and Stages II and III A/B myeloma by Durie-Salmon stage. Stage IA becomes smoldering or indolent myeloma.

^aIf no monoclonal protein is detected (nonsecretory disease), then $\geq 30\%$ monoclonal bone marrow plasma cells and/or a biopsy-proven plasmacytoma required.

^bA variety of other types of end organ dysfunctions can occasionally occur and lead to a need for therapy. Such dysfunction is sufficient to support classification as myeloma if proven to be myeloma-related.

^cIf a solitary (biopsy-proven) plasmacytoma or osteoporosis alone (without fractures) are the sole defining criteria, then $\geq 30\%$ plasma cells are required in the bone marrow.

Reference:

*Myeloma management guidelines: a consensus report from the Scientific Advisors of the International Myeloma Foundation. *The Hematology Journal* 2003;4:379-398

16.3 Appendix C: Uniform Response Reporting Criteria for Multiple Myeloma by the International Myeloma Working Group (IMWG)

Response subcategory	Response Criteria
sCR ¹	
 CR as defined below plus normal FLC ratio and absence of clonal cells in bone marrow by immunohistochemistry or 2- to 4-color flow cytometry
CR ²	
 Negative immunofixation of serum and urine, disappearance of any soft tissue plasmacytomas, and < 5% plasma cells in bone marrow
VGPR ²	
 Serum and urine M-protein detectable by immunofixation but not on electrophoresis or ≥ 90% reduction in serum M-component plus urine M-component < 100 mg per 24 hours

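### The secondary objective is a CR rate to maintenance, but the analysis plan names only overall and best response rates in all 30 patients, with no CR rate and no pre-maintenance reference

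*Combined protocol and SAP*

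**What the plan says.** - **Objective (Section 4.2).** "To evaluate the complete response rate to panobinostat maintenance therapy after autologous HCT".
- **Analysis (Section 13.1).** "We will compute the overall response rates before the transplant, after autologous HCT, and after the completion of maintenance therapy, and at best response". Proportions get two-sided Clopper-Pearson 95% intervals. The denominator rule is "All 30 patients are eligible for secondary endpoints".
- **Restated objectives (Section 13.1.4).** The response and survival parameters become "overall response rate, best response rate, 2-year PFS and 2-year OS". CR is not among them. Elsewhere in Section 13, CR appears only in 13.1, where absence of CR before transplant picks out the patients best suited to the T-effector analysis.
- **Association model (Section 13.1.4).** For the exploratory markers (MRD, B cell precursors, immune response), the planned association analysis reads "with response, PFS and OS will be evaluated using the Cox proportional hazards regression model".
- **Entry condition (Section 6.1.3, criterion 6).** The criterion opens "Patients must have achieved at least PR prior to autologous HCT and must not have progressive disease (PD"; its second condition runs up to the start of maintenance.
- **Categories (Section 8.2 and Appendix C).** Each response is classified by IMWG category. CR requires "Negative immunofixation of serum and urine, disappearance of any soft tissue plasmacytomas, and < 5% plasma cells in bone marrow".
- **Restaging (Section 8.2).** All subjects are restaged every 3 months as standard of care, "including serum protein electrophoresis (SPEP), urine protein electrophoresis (UPEP) and serum free light chains", with response assessed at about cycles 3, 6, 9 and 12.

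**The concern.** The objective asks what maintenance adds: how many patients reach CR on panobinostat. Patients enter after induction and transplant with at least a PR already recorded, so much of their response precedes the drug. An overall response rate may be close to its ceiling before the first dose. A CR rate over all 30 would include CRs produced by earlier treatment.

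Section 13.1 does list an after-transplant time point, but does not make it the reference for response to maintenance. It does not say when the best-response window opens, or how patients already in CR are handled. Two analysts following the text could report quite different figures, and neither need answer the objective.

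The Cox model is a separate mismatch. It needs a time to event, and response is defined only as a category at scheduled assessments.

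**Working it through.** **1. The plan's own precision figures.** Section 13.1 gives 95% interval widths of 0.356, 0.438, 0.487, 0.514 and 0.522 for completion proportions 0.9, 0.8, 0.7, 0.6 and 0.5. The Clopper-Pearson limits are the 0.025 quantile of Beta(x, n−x+1) and the 0.975 quantile of Beta(x+1, n−x). With n = 15 and x = 15p (non-integer allowed), the widths are 0.3561, 0.4376, 0.4868, 0.5138 and 0.5224. The plan's figures reproduce. They concern the primary endpoint; no precision is given for any response rate.

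**2. What overall response probably means.** Section 13 does not define it. In Table 2-4, the clinical benefit rate is MR or better. In the two trials reporting all three figures, its excess over the overall response rate equals the MR rate:
- 61.3 − 51.6 = 9.7, and MR is 9.7
- 52.7 − 34.5 = 18.2, and MR is 18.2

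So the background uses overall response for PR or better. Carrying that into Section 13 is an inference.

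**3. Consequence before transplant.** On that reading, criterion 6 fixes the pre-transplant rate at 30/30 = 100% (exact 95% CI 88.4 to 100). At maintenance start it is not fixed, because only absence of progression is required by then.

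**4. Insensitivity to deepening.** Assumptions not in the documents: 40% in CR at maintenance start, and 2 of 30 below PR at both start and end. Then 30 × 0.4 = 12 are in CR, 30 − 12 = 18 are not, and 18 − 2 = 16 are in PR or VGPR.

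| Scenario | Overall response at end | Conversion to CR |
|---|---|---|
| Nobody deepens | 28/30 = 93.3% (77.9 to 99.2) | 0/18 = 0% (0 to 18.5) |
| All 16 deepen | 28/30 = 93.3% (77.9 to 99.2) | 16/18 = 88.9% (65.3 to 98.6) |

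The two rows are extremes, chosen to show that the statistic cannot tell them apart. They are not forecasts.

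**5. A CR rate over all 30.** With no conversion and no loss of CR, it equals the share already in CR at the start:
- 20% assumed: 6/30 = 20% (7.7 to 38.6)
- 40% assumed: 12/30 = 40% (22.7 to 59.4)
- 60% assumed: 18/30 = 60% (40.6 to 77.3)

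**6. One data set, three answers.** Take 12 in CR at the start and 3 new CRs (assumed):
- CR at end, all patients: (12 + 3)/30 = 50.0% (31.3 to 68.7)
- new CRs over all patients: 3/30 = 10.0% (2.1 to 26.5)
- conversion among those not in CR at the start: 3/18 = 16.7% (3.6 to 41.4)

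The text does not say which is the CR rate to maintenance.

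**The case against.** The strongest reply is that little is missing. Section 8.2 classifies every response by Appendix C category, so CR status will be recorded. Section 13.1 supplies a denominator, an interval method and time points that include after transplant and after maintenance, and Section 5 says response will be evaluated after completion of treatment. The plural in 13.1 could mean response by category, and best response is a natural reading of a response rate to maintenance. The endpoint is descriptive, in 30 non-randomised patients.

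Much of this stands, and it limits the point. The data needed are largely scheduled, and PR or better remains an inference. What survives is that no CR rate is named, no reference is designated, and the all-30 denominator mixes CRs from before and after the first dose.

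A reader might infer more than the documents support:
- **That CR cannot be established on study.** Section 8.2 introduces its tests as inclusions within standard-of-care restaging, so immunofixation and clinical marrow are not excluded. The marrow row in Table 8-1 covers research samples only. The plan is silent on whether these tests are done.
- **That early stoppers have no end assessment.** The end-of-study visit in Table 8-1 is dated from cycle 12, but 8.2 restages all subjects every 3 months and 8.3.4 refers to a treatment completion visit.
- **That CR needs a repeat assessment.** Appendix C, as reproduced, does not require one.

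**Conclusion.** The point holds as a mismatch between objective and analysis. Followed as written, Sections 13.1 and 13.1.4 do not commit the trial to a CR rate, and neither an overall response rate nor a CR rate over all 30 isolates what maintenance adds. Using Cox regression for response is a clear model mismatch.

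The possible size is large for this endpoint: an unchanged 93.3% can accompany 0% or 88.9% conversion, and one data set can yield 10% to 50%. These sizes rest on assumed counts (20 to 60% in CR at maintenance start, 2 of 30 below PR, 3 new CRs), and the 93.3% comparison also rests on reading overall response as PR or better. The missing CR rate and reference, and the Cox mismatch, depend on none of these.

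The reach is limited to a descriptive secondary endpoint and an exploratory association. The completion-rate analysis and sample size are untouched, and PFS, OS and MRD remain as other read-outs. The change should be made, but the trial's main conclusion does not depend on it.

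**What to change.** In Sections 13.1 and 13.1.4:

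1. Name the CR+sCR rate, by Appendix C category, at the last assessment before cycle 1 and at end of maintenance, in all patients. Specifying the last assessment matters: Table 8-1 allows enrolment from day +45 and cycle 1 up to day +180, a gap of up to 180 − 45 = 135 days.
2. As the estimate for the 4.2 objective, report the proportion reaching CR/sCR as best response from maintenance start, and at end of maintenance, among patients not in CR at that pre-maintenance assessment. Give Clopper-Pearson 95% intervals and count patients with no post-baseline assessment as not converted.
3. Count best response from maintenance start only, and state which categories make up overall response.
4. Use exact or logistic methods for associations with response; keep Cox for PFS and OS.

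As a secondary matter, state whether standard-of-care restaging includes the immunofixation and marrow plasma-cell percentage that Appendix C requires, and label CRs lacking them as unconfirmed. Reconcile Section 9.3, which mentions a cycle 6 marrow, with Tables 8-1 and 9-1, which do not carry one.

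**Cost.** Mostly wording, plus a clarification in 8.2 or Table 8-1. The statistical price is a smaller denominator. At an assumed one-third conversion, the exact interval width is 39.7 points for 8/24, 45.7 for 6/18 and 55.2 for 4/12 (20%, 40% and 60% already in CR), against 35.5 for 10/30. Per cohort the widths are 55.2 (4/12), 62.6 (3/9) and 73.4 (2/6), so cohort figures are descriptive only. Counting unassessed patients as not converted may understate conversion.
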